PRIMARY OBJECTIVE

To compare 2-week post-injury assessments of patient reported pain of participants undergoing operative versus non-operative treatment following a lateral compression type pelvic fracture. We hypothesize that there will be a decrease in the Visual Analog Scale (VAS) pain scores in the operative group as compared to the non-operative group both during their hospital stay and in the short-term outpatient follow up.

SECONDARY OBJECTIVES

To compare assessments of narcotic use up to 1 year post injury of participants undergoing operative versus non-operative treatment following a lateral compression type pelvic fracture. We hypothesize that there will be a decrease in the narcotic requirements in the operative group as compared to the non-operative group throughout the 1 year follow up.

To compare assessments of time to first mobilization (bed to chair) with physical therapy of participants undergoing operative versus non-operative treatment following a lateral compression type pelvic fracture. We hypothesize that the operative group will mobilize out of bed to chair with physical therapy faster than the non-operative group.

EXPLORATORY OBJECTIVES

To explore associations between treatment and:

1. Hospital length of stay (index hospitalization)
2. Work productivity and activity impairment up to 1 year post injury
3. Health related quality of life up to 1 year post injury
4. Pelvic specific functional outcome up to 1 year post injury.

DESCRIPTION OF THE STUDY DESIGN

The Pelvis RCT study is a prospective randomized treatment trial to evaluate outcomes among operative versus non-operative lateral compression type fractures. If the patient does not agree to randomization, the patient will be asked to participate in the observational arm of the study. A schematic representation of participant enrollment can be found in the figure below.

A total of 130 patients will be enrolled (65 per arm). University of Maryland, Shock Trauma Center will act as the coordinating center for this study and all patient will be recruited from

University of Maryland, Shock Trauma Center and Indiana University Health Methodist Hospital.

Patients and/or the patient's legally authorized representative (LAR) will be approached for informed consent as soon as is feasible following determination of eligibility.

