Our primary hypothesis is that the operative treatment group will have lower VAS pain scores compared to the non-operative treatment group both during their hospital stay and in the short-term outpatient follow-up.

Based on the results of a pilot study, we expect pain scores in the non-operative group to have a mean of 5.7 and a standard deviation of 2.3. Assuming a 20% reduction in pain scores, 130 patients (65 per arm) are required to have an 80% chance of detecting, as significant at the 5% level, a decrease in the primary outcome measure from 5.7 in the control group to 4.56 in the experimental group. This is our primary outcome and the study will be powered for this variable.

Primary data analysis will involve direct comparison of the change in value of the reported pain scores at the time points listed below. We will be powered to detect a 20% reduction in pain. Secondary analysis will compare the value of narcotics administered at the distinct time periods. Tertiary analysis will be comparing the time (in days) to mobilization with physical therapy. The previous retrospective pilot study incorporated a propensity factor, generated from well documented sources of pain. As this is a prospectively randomized trial, we do not anticipate needing to accommodate for matching.

RANDOMIZATION

Eligible patients will be randomized in equal proportions to one of the two treatment groups: 1) operative treatment of the lateral compression type fracture, 2) non-operative treatment of the lateral compression type fracture. Allocation will be concealed using a centralized 24-hour computerized randomization system, www.randomize.net, that will allow Internet based allocation. The treatment allocation will be stratified on the following prognostic factors to ensure balance between the intervention groups: 1) patient intubation status at time of enrollment, 2) patient prescription pain medication usage during the month prior to injury.

DATA MANAGEMENT

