**Pelvis RCT: Impact of Surgery on Pain in Lateral Compression Type Pelvic Fractures**

**NCT: 02625766**

**December 28, 2020**

### Statistical Analysis

[figure not shown]
The primary analyses were based on the intent-to-treat principle. The primary analysis for pain and secondary analysis for functional outcome estimated the difference in the average treatment effect based on a longitudinal assessment within the initial 12-weeks after the fracture. This approach uses each patient's multiple outcome assessments to compare the average pain and function experienced over the 12-week period between the treatment groups. For these analyses, we used a Bayesian hierarchical model that applied a prior probability of no treatment difference based on the conflicting evidence in the prior literature [3-6]. This is akin to an initial assumption that there is "no difference" in pain or functional outcome between the treatment groups. In addition to estimating the average treatment effect, we calculated the posterior probability (meaning conditioning the prior distribution on the data at hand) of treatment benefit with operative treatment under various minimally clinical important difference (MCID) thresholds. The models included a dummy variable for each patient as a random intercept, an autoregressive correlation structure, and adjusted for whether the treatment was randomly assigned, the patient's pre-injury narcotic use, and a time-varying covariate that measured narcotic use at each time point. Multivariable linear regression was used to analyze the treatment effect on hospital length of stay and time to mobilization. Outcome data were missing in 16% of the sample at 2-weeks, and 14% of the sample at 6-weeks and 12-weeks, and was therefore imputed using multiple imputation for the final models [16]. To assess possible effect measure modification based on the initial degree of displacement, we stratified the sample to create two subgroups, patients with  $\geq 5$ mm of displacement and patients with  $< 5$ mm of displacement. We then calculated the average effect of operative treatment on pain in each of the subgroups. In addition, we compared the average treatment effect of operative fixation on pain with posterior-only fixation compared to operative fixation with anterior and posterior fixation. Additional sensitivity analyses recalculated the pain and function outcomes to separately compare the treatment effects between patients enrolled in the randomized cohort and the observational cohort. The analyses were performed using R Version 3.6.1 (Vienna, Austria) with the packages *lme4*, *rstan*, *brms*, and *mice*.

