
We took two critical steps to understand the potential for biased treatment estimates from pooling the results from the randomized and non-randomized participants. First, we performed sensitivity analyses to separately examine the results for the randomized and non-randomized cohorts. These analyses suggested similar (or even larger) estimated treatment benefits from surgery within the RCT data. Second, we included willingness to be randomized as a potentially confounding variable in our final analysis models, despite there being no evidence that it affected treatment.

[figure not shown]
The ability to assess the probability of different magnitudes of treatment benefit is a unique characteristic of Bayesian data analysis, and is not possible with traditional non-Bayesian statistical hypothesis testing. Despite this inherent difference in statistical principles, it should be noted that the average treatment benefits reported from our Bayesian analysis are nearly identical to the results obtained using traditional multilevel linear regression models (results not reported).

Additional results from the described analyses, that were not included in the main article, are provided below.

[figure not shown]
**Posterior probability of reduced pain.** Posterior probability of reduced pain with operative treatment within 12 weeks of injury.

[figure not shown]
**Mean pain stratified between randomized and nonrandomized patients.** The mean Brief Pain Inventory scores and 95% credible intervals within the initial 12-weeks of injury for minimally displaced complete lateral compression pelvis fracture patients. The patients are stratified based on their study type (randomized trial versus observation) and treatment type (operative versus nonoperative treatment). The pain scores are adjusted for the study type, prior narcotic use, and narcotic use at each time point.

**Posterior probability of improved function.** Posterior probability of improved function, measured with the Majeed score, with operative treatment within 12 weeks of injury.

**Mean function stratified between randomized and nonrandomized patients.** The mean Majeed scores and 95% credible intervals within the initial 12-weeks of injury for minimally displaced complete lateral compression pelvis fracture patients. The patients are stratified based on their study type (randomized trial versus observation) and treatment type (operative versus nonoperative treatment).

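### The listed terms of the primary longitudinal model include narcotic use at each visit but no visit effect; fitted that way, the treatment effect is biased whenever narcotic use differs between arms

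*SAP*

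**What the plan says.** The SAP (Statistical Analysis) uses a Bayesian hierarchical model for pain and function, whose purpose is to "compare the average pain and function experienced over the 12-week period between the treatment groups". It names these terms:

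- "The models included a dummy variable for each patient as a random intercept, an autoregressive correlation structure";
- "adjusted for whether the treatment was randomly assigned, the patient's pre-injury narcotic use";
- "a time-varying covariate that measured narcotic use at each time point".

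The caption to the SAP figure of mean pain by cohort repeats the adjustment set: "The pain scores are adjusted for the study type, prior narcotic use, and narcotic use at each time point". Neither place mentions a visit or time effect, or a treatment-by-visit term. The model formula is not given.

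On completeness the SAP reports: "Outcome data were missing in 16% of the sample at 2-weeks, and 14% of the sample at 6-weeks and 12-weeks". These data were multiply imputed.

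The protocol (Secondary Objectives) expects treatment to change the covariate: "We hypothesize that there will be a decrease in the narcotic requirements in the operative group". Under Secondary Endpoints it says narcotic use will be converted to morphine equivalents. The SAP does not say how the covariate was coded.

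**The concern.** With balanced visits and only baseline covariates, leaving visit out does not move the treatment coefficient, because every patient contributes the same visits in both arms. A time-varying covariate changes that. Pain and narcotic use can both be expected to fall between 2 and 12 weeks. If visit is not in the mean model, the within-patient association between the two mixes the real pain–narcotic relation with ordinary recovery, and the narcotic coefficient comes out too large. The autoregressive structure does not prevent this, since it describes residual correlation and not the mean trend.

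An inflated narcotic coefficient does no harm to the treatment comparison while the arms use narcotics equally. If they do not, the model removes too much of the between-arm difference in pain, or adds too much to it. The primary result is reported as posterior probabilities of exceeding several benefit thresholds, and these can move noticeably with a small shift in the mean. The same list of terms covers the functional outcome.

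**Working it through.** **The plan's own figure.** The documents give no number for this point. The scale comes from the sample size (Protocol, Data Analysis): "we expect pain scores in the non-operative group to have a mean of 5.7 and a standard deviation of 2.3", with a 20% reduction to 4.56, so the design effect is 5.7 − 4.56 = 1.14. With two-sided 5% (sidedness is not stated) and 80% power, n per arm = 2 × (1.960 + 0.842)² × 2.3² / 1.14² = 63.9, so 64 per arm or 128 in total. At 65 per arm the power is 80.7% (normal) or 80.1% (noncentral t). The planned 130 reproduces, and 1.14 is used below as the yardstick.

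**Relation used.** With balanced visits, approximately:

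fitted treatment coefficient ≈ total effect − (fitted narcotic slope) × (operative minus non-operative narcotic use).

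Hence the shift from leaving visit out ≈ −(slope without visit − slope with visit) × (arm difference).

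**Calculation 1: narcotic use as a continuous score.** Assumed: three visits, random-intercept SD 1.6 and residual SD 1.65 (1.6² + 1.65² = 5.28, close to 2.3² = 5.29), residual autocorrelation 0.4, direct treatment effect −1.14, true narcotic slope 0.30, and narcotic use falling 2 units over follow-up. The fit is generalised least squares, averaged over large simulated samples. With visit in the model, the narcotic slope is about 0.30 throughout. Without visit:

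| Fall in pain over follow-up | Narcotic slope | Shift, arm difference 0 | −0.25 | −0.5 | −1.0 |
|---|---|---|---|---|---|
| 1 point | 0.55 | about 0 | +0.06 | +0.12 | +0.25 |
| 2 points | 0.80 | about 0 | +0.11 | +0.26 | +0.50 |
| 3 points | 1.05 | about 0 | +0.19 | +0.37 | +0.74 |

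Check against the relation: with an arm difference of −0.5, the total effect is −1.14 + 0.30 × (−0.5) = −1.29. With slope 0.80, the expected coefficient is −1.29 − 0.80 × (−0.5) = −0.89; the fitted value is −0.88. With visit it is −1.14. Without the narcotic covariate it is −1.29, with or without visit.

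**Calculation 2: narcotic use as yes/no, random intercept plus AR(1).** Assumed: pain 5.5, 4.0 and 2.8 at 2, 6 and 12 weeks; narcotic users 85%, 50% and 25%; true narcotic coefficient 0.5; direct effect −1.14; random-intercept SD 1.5, residual SD 1.6, autocorrelation 0.3; maximum likelihood.

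- With visit, the narcotic coefficient is about 0.5. Without visit it is about 1.4 if the pain values are taken as non-operative means, and about 1.5 if narcotic use adds to them.
- Operative use 10 points lower: shift ≈ (1.4 − 0.5) × 0.10 = 0.09 to (1.5 − 0.5) × 0.10 = 0.10.
- Operative use 20 points lower: shift ≈ (1.4 − 0.5) × 0.20 = 0.18 to (1.5 − 0.5) × 0.20 = 0.20. The fitted models give 0.19 and 0.21.
- As a share of the design effect: 0.09 / 1.14 = 8% and 0.19 / 1.14 = 17%.
- With no arm difference, the shift is essentially zero.
- With a random intercept only, the shifts for 10, 15 and 20 points are about 0.14, 0.21 and 0.28. Dropping the SAP's autoregressive term therefore overstates the problem.

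**What 0.1 to 0.2 point could do to a reported probability.** The SAP gives 0.9 (0.1 to 1.8) for displacement below 5 mm. A normal posterior with SD (1.8 − 0.1) / 3.92 = 0.43 reproduces the reported 98%, 82%, 41%, 8% and 1%. Hold that SD fixed and assume the subgroup model carries the same covariates. If the true mean is higher by 0.1 or 0.2, the probability of a benefit above 1.0 moves from 41% to 50% or 59%. If it is lower by 0.1 or 0.2, the probability moves to 32% or 24%.

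**The case against.** The strongest reply is that the premise rests on silence. One prose sentence is not a specification: it does not list the treatment term either, and treatment was plainly in the model. An autoregressive structure needs visits in time order, so time was at least in the data set. This stands. A reader might infer that visit was left out of the fitted model, but the documents support only that it is not among the listed terms.

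A reader might also infer that the reported treatment effect is distorted. That does not follow. Distortion needs an arm difference in narcotic use. The documents contain a hypothesis about this, without a size, and no narcotic results. If the hypothesis is right, the bias is toward the null and a finding of benefit is conservative. A shift of 0.1 to 0.2 is also small beside a subgroup interval running from 0.1 to 1.8.

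The inputs to the calculations are assumed throughout, and a constant 20-point gap is extreme, since it would mean 5% against 25% users at 12 weeks. That also stands, so the magnitudes are illustrative.

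One possible defence does not help. The SAP says conventional multilevel regression gave nearly identical results, but those results are not shown and their covariates are not stated. If they used the same terms, they would share the same bias. The separate analyses of the randomised and observational cohorts address pooling, not the time trend.

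**Conclusion.** The point holds in conditional form. The mechanism is confirmed under two codings of narcotic use. The condition that turns it into bias, a difference in narcotic use between arms, is what the protocol itself hypothesises, though the opposite direction cannot be excluded. With the SAP's correlation structure, a plausible size is roughly 0.1 to 0.2 point for a 10 to 20 percentage-point difference. That rests on assumed visit means, prevalences, slope and variances, and the true size cannot be derived from the documents.

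It would be wrong to conclude that adding visit settles the matter. Narcotic use is measured after treatment, so a visit-adjusted model that keeps it still estimates a direct effect. In the yes/no example with a 20-point gap, the total effect is −1.14 + 0.5 × (−0.20) = −1.24, while the model with visit and narcotic use returns about −1.14.

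**What to change.** State the full model formula for pain and function, including whether visit was a fixed effect and how narcotic use was coded. Fit the model with visit (2, 6 and 12 weeks) as a categorical fixed effect, which adds two parameters. Report the treatment effect from that model both with the narcotic covariate and without it; the version without it gives the total effect. Report mean narcotic use by arm and visit, so that readers can judge the direction and size of any shift.

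A treatment-by-visit term (two further parameters) is optional. It would give the protocol's 2-week contrast and the 12-week average from one model, but it is not needed to remove this bias.

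The cost is a few parameters and a refit on the existing imputed data. If visit was already in the model, the first part needs only a sentence.

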Study duration: We will recruit for a year and a half. Patients will be followed for 1 year. We estimate 4 years total.

Primary outcome measure: *Pain* as measured by using the arithmetic mean of the four pain severity items on the patient-reported Brief Pain Inventory assessment (BPI) 2-weeks following the patient's injury.

Secondary outcome measures: *Length of stay* will be determined by recording the admission date versus discharge date for the patient's index hospitalization. *Time to first mobilization (bed to chair)* will be determined using the physical therapy notes during the patient's index hospitalization and is defined as days post-injury and days post-operative treatment (if applicable) to time of first mobilization (bed to chair). *Narcotic use* will be determined by cross-referencing the patient's medical record during the index hospitalization and follow-up clinic appointments with patient-reported usage. *Work productivity and impairment* will be determined using the modified WPAI:SHP questionnaire. *Health related quality of life* will be measured using the VR-12 questionnaire. *Pelvic function* will be measured using the Majeed Pelvic Score.

Statistical analysis: We are interested in estimating the causal effect of operative treatment versus non-operative treatment in lateral compression type pelvic fracture patients. For all our

analyses, we will report estimates of the causal effects, standard errors, and confidence intervals. We will also report the results of tests of null hypothesis of no causal effect.

KEY ROLES

Safety Monitor- [name] will be responsible for overseeing patient safety for the study. [name] will review the enrollment numbers and medical compliance annually for the duration of the study.

Coordinating Center Principle & Sub-Investigators- [name] [name] (PI) and the sub-investigators will be responsible for developing a detailed study protocol, providing oversight on study progress and act to correct deficiencies in the conduct of the study. The PI and sub-investigators will also draft the main publications related to the study, and assist with patient consent.

Site Principle & Sub-Investigators- The site PI and sub-investigators will be responsible for oversight on local study progress. The site PI and sub-investigators will also contribute to the main publications related to the study, and assist with patient consent.

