During the index hospitalization, participants will be asked to provide basic demographic information, health status and function prior to injury. Study injury characteristics will be obtained from the surgeon and the participant's medical record.

Participants will be prospectively followed at 2 weeks, 6 weeks, 3 months and 1 year post-injury. All follow-ups will occur in person at the hospital clinic follow-ups or over the phone and will consist of both a clinical examination (when applicable) and interview.

[figure not shown]

Figure: Participant Enrollment

PRIMARY ENDPOINT

The primary endpoint is *patient reported pain severity* as measured by the Brief Pain Inventory assessment (BPI). The BPI is a 15-item questionnaire that assesses the severity of pain, the impact of pain on daily function, the location of pain, pain medications and the amount of pain relief. There is no scoring algorithm but the arithmetic mean of the four severity items can be used as a measure of pain severity and the arithmetic mean of the seven interference items can be used as a measure of pain interference. This assessment has been chosen because it is a short, reliable, patient reported assessment of pain that has been specifically designed for and validated in patients with pain from acute conditions such as postoperative pain.

SECONDARY ENDPOINTS

The secondary endpoints include:

1. *Length of stay.* This will be found in the patient's medical record using the admission date and time versus the discharge date and time during his/her index hospitalization.
2. *Time to first mobilization (bed to chair).* This will be found in the patient's medical record during his/her index hospitalization. Data will be found in the physical therapy notes and will be recorded as days post-injury and days post-operative treatment if applicable.
3. *Patient reported narcotic use.* This is will be recorded by cross-referencing the patient's medical record and patient-reported questionnaire about pain medication use. The total narcotic use will be converted to the morphine equivalent for statistical analysis.

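### The primary pain model adjusts for narcotic use at each follow-up visit, a secondary outcome surgery is hypothesised to lower, so it does not estimate the total effect of surgery on pain.

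*SAP*

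**What the plan says.** **Target.** The Protocol Summary (Statistical analysis) states: "We are interested in estimating the causal effect of operative treatment versus non-operative treatment". The SAP (Statistical Analysis) says its primary pain analysis estimates an average treatment effect over the first 12 weeks, and adds: "The primary analyses were based on the intent-to-treat principle".

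**Model.** The SAP lists three adjustments: whether treatment was randomly assigned, pre-injury narcotic use, and "a time-varying covariate that measured narcotic use at each time point". The sentence is about the models in the plural, so the function model apparently carries the same term, although the legend of the Majeed figure does not mention it. For pain, the legend of the figure split into randomised and nonrandomised patients confirms it: "The pain scores are adjusted for the study type, prior narcotic use, and narcotic use at each time point".

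**Role of narcotic use in the protocol.** It is an outcome throughout. Secondary Objectives: "We hypothesize that there will be a decrease in the narcotic requirements in the operative group as compared to the non-operative group". Secondary Endpoints: "The total narcotic use will be converted to the morphine equivalent for statistical analysis". Data Analysis plans a secondary comparison of narcotics at the distinct time periods. The protocol nowhere gives follow-up narcotic use the role of a covariate.

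**The concern.** Narcotic use at the follow-up visits comes after treatment and can be changed by it. It can relieve pain at the same visit. It is also plausibly driven by that pain; this is an inference, not something the documents state. Holding it fixed removes any part of the effect that runs through narcotic use. If pain drives use, it also removes part of the pain difference itself. What remains is not the total effect. Nor is it a clean direct effect, because pain and narcotic use can share causes. Neither document defines an effect at equal narcotic use as the estimand.

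The coefficient feeds the main pain difference and the posterior probabilities of exceeding each threshold. The SAP's sensitivity analyses split the randomised from the observational cohort, and the pain legend for that split states the same adjustment, so the split does not remove the problem.

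**Working it through.** **1. Inputs from the protocol (Data Analysis).** Control mean 5.7, SD 2.3, target mean 4.56, so the planned reduction is 5.7 − 4.56 = 1.14. These reproduce the stated sample size: n per arm = 2 × (1.960 + 0.842)² × 2.3² / 1.14² ≈ 64, and the t-test version gives 64.9, hence 65 per arm and 130 in total. The sample size is not in dispute; the 1.14 and 2.3 are reused below.

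**2. Inputs not in the documents (assumed).** The within-arm correlation r between pain and narcotic use at a visit, and the effect of surgery on use.

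**3. One visit.** Let P = δT + u be pain, T treatment, and N = bP + γT + e narcotic use, scaled to within-arm SD 1, so b = r/SD.
- Arm difference in N: a = rδ/SD + γ.
- Within-arm slope of P on N: β = r × SD.
- Adjusted coefficient = δ − aβ = δ(1 − r²) − r × SD × γ.

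With δ = −1.14 and SD = 2.3:

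| r | γ = 0: use only follows pain | γ = −0.5: surgery also lowers use at equal pain | γ = +0.5: surgery raises use at equal pain |
|---|---|---|---|
| 0.3 | −1.14 × 0.91 = −1.04 | −1.04 + 0.345 = −0.69 | −1.04 − 0.345 = −1.38 |
| 0.4 | −1.14 × 0.84 = −0.96 | −0.96 + 0.46 = −0.50 | −0.96 − 0.46 = −1.42 |
| 0.5 | −1.14 × 0.75 = −0.86 | −0.86 + 0.575 = −0.28 | −0.86 − 0.575 = −1.43 |

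(Sums use unrounded values.)

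**4. Pure mediator (alternative to step 3; needs a negative association).** Suppose narcotics relieve pain by 0.6 points per SD and surgery lowers use by 0.5 SD. The path through narcotics is (−0.5) × (−0.6) = +0.30. The adjusted coefficient is −1.14 − 0.30 = −1.44, so the benefit is overstated.

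**5. Three visits.** A linear model with random intercept and AR(1) errors was fitted by maximum likelihood to simulated data: 20,000 patients per setting (12,000 at r = 0.5), ICC 0.3 to 0.6, residual autocorrelation 0 or 0.4, within-patient correlation of the narcotic residual 0 or 0.5. The SAP supports a multilevel linear model as a stand-in, since it calls its average benefits "nearly identical to the results obtained using traditional multilevel linear regression models".
- With γ = 0, a reduction of 1.14 is reported as 1.03–1.10 (r = 0.3), 0.94–1.07 (r = 0.4) or 0.82–1.02 (r = 0.5).
- With γ = ±0.5, there is a further shift of about 0.14–0.39 (r = 0.3) or 0.19–0.51 (r = 0.4): against surgery when γ is negative, in its favour when positive.
- The mediator case again gives about 1.44.

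**6. Effect on the threshold probabilities.** The SAP's displacement table gives, below 5 mm, a mean difference of 0.9 (95% CrI 0.1 to 1.8). A normal posterior with SD (1.8 − 0.1)/3.92 = 0.434 yields 98.1, 82.2, 40.9, 8.3 and 0.6% for thresholds 0, 0.5, 1.0, 1.5 and 2.0. The table reports 98, 82, 41, 8 and 1%, so the approximation reproduces that column. Moving the mean:

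| Shift in mean | P(reduction > 1.0) | P(reduction > 0) |
|---|---|---|
| −0.3 | 18% | 92% |
| −0.1 | 32% | 97% |
| none | 41% | 98% |
| +0.1 | 50% | 99% |
| +0.3 | 68% | >99% |

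This assumes that the subgroup models use the listed covariates.

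**The case against.** - **The size is assumed.** The documents give neither the arm difference in narcotic use nor its association with pain. At r = 0.1 or 0.2 with γ = 0, the one-visit shift is only 1.14 × 0.01 = 0.01 or 1.14 × 0.04 = 0.05 points. The larger figures need surgery to change use at equal pain, whereas the protocol hypothesises only lower use overall, which could come entirely through less pain. This stands: the bias is possible in either direction, and its size is not shown.
- **The threshold example is the sensitive one.** A cut-off of 1.0 lies next to the mean of 0.9. P(reduction > 0) in the same column falls only from 98% to 97% or 92%. At 5 mm or more, P(reduction > 1.0) falls from about 97% to 95% or 91%; there the normal approximation also fits less well (85% and 62% against the reported 88% and 65% at 1.5 and 2.0). This also stands: sensitivity depends on the threshold.
- **Intent-to-treat mainly means analysis by assigned group.** True, so that sentence alone does not contradict the covariate. The stronger basis is the protocol's causal target together with the SAP's average treatment effect.
- **Dropping the covariate could alter confounding.** In the pooled, partly non-randomised sample, which may include polytrauma patients, narcotic use may also stand in for pain from other injuries. This is a reason to show the randomised-only result without the covariate, where that argument does not apply.
- **The SAP is dated December 2020 and already reports results.** Changing the primary model now is post hoc and must be labelled so. But the protocol itself gave narcotic use only the role of an outcome.
- **The main article may report a model without the covariate.** It was not available here. The non-Bayesian comparison is unreported and is not said to omit the term.

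None of this makes the adjusted coefficient the total effect.

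**Conclusion.** Wrong as written. The primary pain model, and apparently the function model, conditions on a post-treatment variable that the protocol treats as an outcome, while the stated target is the causal average effect of treatment. This follows from the text and does not depend on any assumed number.

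The consequence for the estimate is not fixed by the documents. Under the assumptions shown, a true reduction of 1.14 could be reported as moderately smaller, much smaller, or larger (about 1.44 in the mediator case). There is no shift if surgery does not change narcotic use at the visits, or if use is unrelated to pain within arm. The figures illustrate sensitivity; they are not operating characteristics of the pooled Bayesian model.

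**What to change.** 1. Make the model without the time-varying narcotic term primary for pain and for function. Keep pre-injury narcotic use and the study-type term, which the SAP describes thus: "we included willingness to be randomized as a potentially confounding variable in our final analysis models".
2. Report the randomised-only analysis without the narcotic term as well. Removing the term does not by itself resolve confounding among the observational patients.
3. Analyse narcotic use as its own outcome in morphine equivalents, as the protocol states.
4. Keep the narcotic-adjusted model as a labelled supplementary analysis, and print both sets of mean differences and posterior probabilities side by side.
5. Say openly that the change was made after results were known.

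A separate minor point, on precision rather than this bias: intubation status at enrolment, the other stratification factor, could be added as a baseline covariate. The protocol collects it on the stratification form (AF03); check that it was also recorded for observational patients before using it in the pooled model.

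The cost is revised SAP wording and a rerun of existing models. No new data are needed and the planned 130 patients do not change. The estimate may move in either direction, or not at all.
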